7.3.3.3. Physical Examination

Abnormal physical examination results will be tabulated by study visit and body system. Physical examination data (including height and weight) will also be listed by scheduled visit.

7.3.3.4. Electrocardiogram

All ECG data will be fully listed and changes from Baseline in ECG data (heart rate, PR interval, RR interval, QRS duration, QT interval) will also be summarized descriptively by scheduled visit. Replicate samples will be averaged in these analyses, using the arithmetic mean.

All QT intervals will be corrected for heart rate according to Fridericia ($QTcF = QT/(RR^{1/3})$). At each time point, the number and percentage of participants falling into the following categories according to the International Conference on Harmonization (ICH) E14 Guidelines will be presented:

- QTc actual values: ≤ 450 ms, >450 to ≤ 480 ms, >480 to ≤ 500 ms, and >500 ms
- QTc increases from Baseline of >30 msec and >60 msec

Changes from Baseline in QTc will also be summarized. Further, ECG data will be classified by the Investigator as “normal,” “abnormal, not clinically significant,” “abnormal, clinically significant” or “indeterminate” at each timepoint assessed. Summary results will include the count and percentage of participants within each category at each visit.

7.4. Pharmacokinetic and Pharmacodynamic Analyses

For PK and PD endpoints, analyses will be performed using the PK and PD Analysis Sets respectively. The PK and PD concentration and parameters, as data permit, will be summarized by cohort.

7.4.1. Pharmacokinetic Concentration Analyses

Plasma concentrations of total molybdenum and PUF molybdenum (as surrogate measures of ALXN1840 PK) vs. time data will be presented in a data listing by participant. Plasma concentration data will be summarized separately by analyte, treatment (dose), day, and time point using the following descriptive statistics: number of participants, arithmetic mean, SD, coefficient of variation (CV), geometric mean (GM), GMCV, 95% confidence interval (CI), median, minimum, and maximum. When calculating the geometric mean, values of 0 will be discarded. For summary statistic calculations, plasma concentration values below the lower limit of quantification (LLOQ) will be set to the LLOQ for analyses using the Full Analysis Set and will be set to 0 for analyses using the PK Analysis Set.

Mean plasma concentration versus scheduled time profiles will be presented in figures on both linear and semilogarithmic scales. Individual plasma concentration versus actual time profiles will be presented similarly. The time to reach steady state will be graphically assessed by plotting mean plasma trough (pre-dose) concentration observed at the start of the dosing interval (C_{trough}) versus study day in both linear and semilogarithmic scales.

7.4.2. Pharmacodynamic Concentration Analyses

Individual ALXN1840 PD and biomarkers, assessed as plasma total copper (PD), PUF copper (PD), LBC (PD), dNCC (PD), Cp (biomarker) and CpC (biomarker) concentration-time data (including measured, absolute change from baseline and percent change from baseline) will be listed by participant.

The PD and biomarker concentration (measured, absolute change from Baseline and percent change from Baseline) data will be summarized separately by analyte, treatment (dose), day, and time point using the following descriptive statistics: number of participants, arithmetic mean, SD, CV, GM, GMCV, median, minimum, and maximum. When calculating the GM, values of 0 will be discarded. For PD and biomarker summary statistic calculations, concentrations below the LLOQ will be set to the LLOQ for analyses using the Full Analysis Set and will be set to 0 for analyses using the PD Analysis Set.

Mean PD and biomarker concentration (measured, absolute change from Baseline and percent change from Baseline) versus scheduled time profiles will be presented in figures on linear scales. Individual PD and biomarker concentration (measured, absolute change from Baseline and percent change from Baseline) versus actual time profiles will be presented similarly.

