2.2. Background

ALXN1840 has been selected for development in WD due to its improved stability properties over ammonium tetrathiomolybdate, which has previously been studied in participants with WD and other indications. Ammonium tetrathiomolybdate and bis-choline tetrathiomolybdate nonclinical and clinical data reported to date support the efficacy and safety of ALXN1840.

ALXN1840 rapidly forms stable tetrathiomolybdate-copper-albumin TPCs, which stabilize free copper leading to a reduction in the NCC concentrations after correction for free copper bound to TPC ($NCC_{corrected}$).

Studies in both healthy and WD animal models showed that treatment with tetrathiomolybdate results in removal of copper from the liver. Tetrathiomolybdate administered to healthy mice by intraperitoneal injection resulted in a dose-dependent reduction in liver copper concentration over a treatment range of 0 - 6 mg/kg/day (human equivalent dose [HED] by body surface area [BSA] scaling: 0 - 1 mg/kg/day). The results of these studies indicated that only 30% - 40% of copper remained after 5 weeks of treatment. Similar liver decoppering (approximately 40% - 60%) was also reported in toxic milk mice (a WD animal model) at 5 mg/kg/day for 14 days (HED by BSA scaling: 0.4 mg/kg/day; Mills, 1981; Czachor, 2002). In LEC WD model rats, 25 mg/kg/day of ALXN1840 (HED by BSA scaling: 4 mg/kg/day) administered by oral gavage for 10 days, resulted in an approximately 50% decrease in liver copper concentration. Because ALXN1840 has been shown to have a similar mechanism of action in healthy and WD animal models, a mechanism of action study in healthy participants is being performed (Study ALXN1840-HV-108) to demonstrate that ALXN1840 can result in a change from baseline in copper balance with repeat-dose ALXN1840 (30 mg/day) treatment.

In the Phase 2 proof-of-concept Study WTX101-201 in participants with WD, ALXN1840 demonstrated a sustained control of free copper as measured by $NCC_{corrected}$. Importantly, ALXN1840 treatment resulted in improvements in disability and neurologic symptoms as measured by the Unified Wilson Disease Rating Scale (UWDRS, Parts II and III) and stabilization of liver function (Weiss, 2017). Treatment with ALXN1840 resulted in an acceptable safety and tolerability profile when initiated at 15 mg daily with Investigator-driven, individual participant titration of dose based on safety, $NCC_{corrected}$, and symptoms.

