Plasma concentrations of total molybdenum and PUF molybdenum vs. time data will be presented in a data listing by participant. Plasma concentration data will be summarized separately by analyte and time point for each treatment by day using the following descriptive statistics: number of participants, arithmetic mean, geometric mean (GM), SD, coefficient of variation (CV), GMCV, median, minimum, and maximum. Mean plasma concentration versus scheduled time profiles will be presented in figures on both linear and semilogarithmic scales. Individual plasma concentration versus actual time profiles will be presented similarly.

Pharmacokinetic parameters derived from plasma concentrations of total molybdenum and PUF molybdenum will be presented in data listings and summarized separately using the following descriptive statistics: number of participants, arithmetic mean, GM, SD, arithmetic CV, GMCV, median, minimum, and maximum. Geometric mean and geometric CV will be presented for C_{\max} and AUCs only.

For PD (total and PUF copper and LBC) and biomarker endpoints (ceruloplasmin, ceruloplasmin-bound copper), concentration-time data will be listed and summarized with descriptive statistics and plotted. The same analyses will be conducted on the absolute and percent changes from baseline of these concentration-time data.

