9.2.6. Change from Baseline

Change from Baseline will be calculated as: post-Baseline assessment value – Baseline assessment value when both values are not missing.

Percent change from Baseline is calculated as (change from Baseline/Baseline result * 100).

If either the Baseline or the post-Baseline result is missing, the change from Baseline and/or percentage change from Baseline is set to missing. Additionally, if the Baseline is 0, the percentage change from Baseline will be missing.

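### SAP 7.4.2 plans geometric means for absolute and percent change from Baseline, where any fall makes them undefined (minor; limited to descriptive PD and biomarker tables)

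*SAP*

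**What the plan says.** SAP 7.4.2 covers six copper-related analytes, "assessed as plasma total copper (PD), PUF copper (PD), LBC (PD), dNCC (PD), Cp (biomarker) and CpC (biomarker) concentration-time data". It treats three forms of each together: "The PD and biomarker concentration (measured, absolute change from Baseline and percent change from Baseline) data will be summarized separately by analyte". The statistics for all three are "number of participants, arithmetic mean, SD, CV, GM, GMCV, median, minimum, and maximum", with no split between measured values and changes. The only rule for values that a logarithm cannot take is: "When calculating the GM, values of 0 will be discarded". The same section sets values below the LLOQ to 0 in the PD Analysis Set and to the LLOQ in the Full Analysis Set.

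SAP 9.2.6 fixes the sign: "Change from Baseline will be calculated as: post-Baseline assessment value – Baseline assessment value when both values are not missing". Percent change inherits it: "Percent change from Baseline is calculated as (change from Baseline/Baseline result * 100".

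Protocol 9.4.4 asks for descriptive statistics on PD and biomarker concentrations and adds: "The same analyses will be conducted on the absolute and percent changes from baseline of these concentration-time data". It names no geometric mean for PD data. For PK parameters, Protocol 9.4.4 and SAP 7.4.3 both limit geometric statistics to C_max and the AUCs. SAP 7.4.2 has no comparable limit.

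**The concern.** The list of statistics suits positive concentrations and has been extended to quantities that can take either sign. Followed literally, it asks for a statistic that does not exist in any cell containing a fall. The zero rule is understandable for concentrations, where a zero stands for a BLQ result. For a change, a zero is a genuine observation of no change, and the rule removes it from the GM.

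Because the SAP is silent on negative values, the programmer has to decide. One choice is to leave the cell empty. Another is to extend the zero rule to everything non-positive. The second would give a number based only on participants whose marker rose, and its sign could be opposite to that of the arithmetic mean in the same table. SAP section 4 says these interim outputs are meant to support regulatory submissions, so the tables should be well defined before they are programmed.

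**Working it through.** The plan gives no figure on this point, so there is nothing to reproduce. The check is by definition, followed by illustrations whose inputs are assumed.

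**Definition.** GM = exp(mean of ln x) and GMCV = sqrt(exp(variance of ln x) - 1). Both need every x > 0. Under SAP 9.2.6, x < 0 for every participant whose value fell and x = 0 for every participant with no change. One negative value per cell is enough to make both undefined.

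**How often the full-cell GM exists.** Let p be the probability that one participant's change is above zero (assumed) and n the cell size. The GM exists for the whole cell with probability p^n. With n = 10 (SAP 9.1 gives approximately 10 participants):

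| p | p^10 |
|---|---|
| 0.25 | 0.0001% |
| 0.50 | 0.10% |
| 0.75 | 5.6% |
| 0.90 | 34.9% |
| 0.95 | 59.9% |

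SAP 7.4 summarises by cohort, so real cells will be smaller. With an assumed n = 5, the values are 0.50^5 = 3.1% and 0.75^5 = 23.7%. The conclusion is the same.

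**If negatives were dropped as well.** Assume percent changes are Normal(m, s) and n = 10. Then p = Φ(m/s), and the chance that no participant rose is (1 - p)^10. The GM of the positive values was averaged over simulated cells with at least one positive value.

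| m | s | p | Chance of no positive value | Mean GM of positives |
|---|---|---|---|---|
| -10% | 30% | 0.37 | 1% | +16% |
| -20% | 30% | 0.25 | 5% | +15% |
| -30% | 30% | 0.16 | 18% | +14% |
| -20% | 15% | 0.09 | 38% | +6% |
| -40% | 20% | 0.02 | 79% | +7% |

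At an SD of 30%, the positives-only GM hardly moves while the true mean goes from -10% to -30%. With a smaller SD or a larger fall, there is often nothing left to summarise. A rise on average does not cure the problem: at m = +30%, s = 30%, p = 0.841 and the full-cell GM is undefined in 1 - 0.841^10 = 82% of cells.

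**Worked example (assumed values).** Take percent changes of -40, -35, -30, -25, -20, -15, -10, -5, +5 and +10.
- Arithmetic mean: -165/10 = -16.5%. Median: -17.5%.
- GM of all ten: undefined.
- GM of the two positive values: sqrt(5 × 10) = +7.1%.
- Geometric mean of the ratios to Baseline (0.60, 0.65, ..., 1.05, 1.10): exp(-1.984/10) = 0.820, that is -18.0%. This is well defined and agrees in sign with the mean and median.

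**The case against.** The strongest reply is that nothing of consequence rests on this statistic.

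- The primary endpoint is average daily copper balance. SAP 7.2.2 names mean plasma total copper and mean LBC as secondary quantities, not a geometric mean of change. No hypothesis is tested.
- SAP 7.4.2 itself also provides the arithmetic mean, median, minimum, maximum, individual listings and linear-scale plots, so the true direction would be visible beside any odd GM.
- SAP 7.4 says summaries are made as data permit, and SAP 7 allows listings alone when numbers are too small.

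Most of this stands, and it sets the severity. The general provisos do not cure the wording, because they do not say how negative values are treated.

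Two stronger readings are tempting, and the documents do not support them. A reader might infer that the plan drops participants whose value fell and will therefore report an effect of the wrong sign. SAP 7.4.2 discards zeros only. Followed as written, a cell with a fall has no GM, which is a visible gap; a wrong-signed number needs an exclusion that the SAP does not contain. A reader might also infer that all six analytes are expected to fall. The Protocol describes a fall for corrected NCC (section 2.2: "leading to a reduction in the NCC concentrations after correction for free copper bound to TPC"), which is not among the six analytes; dNCC is. No expected direction is stated for every analyte, and Protocol 4.2 says that the drug-copper-albumin complex circulates, so a fall in total plasma copper cannot be presumed. The defect does not depend on this, since one negative value in a cell is enough.

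**Conclusion.** The point holds as a minor defect. GM and GMCV are prespecified for absolute and percent change, they are undefined in any cell with a fall, and the zero rule removes genuine no-change results from the GM. No other section of either document resolves this. These conclusions follow from SAP 7.4.2 and 9.2.6 and need no assumption.

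The size of any misleading value does rest on assumptions: normally distributed percent changes, 10 participants per cell, the means and SDs in the tables, and an exclusion of negatives that the SAP does not authorise. The figures of +14% to +16% are an illustration, not a prediction. The effect is confined to descriptive PD and biomarker change tables.

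**What to change.** In SAP 7.4.2:

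1. Restrict GM, GMCV and the discard-zeros rule to measured concentrations.
2. Summarise absolute and percent changes with n, arithmetic mean, SD, median, minimum and maximum.
3. For relative change, report the geometric mean of the post-Baseline/Baseline ratio where both values are quantifiable and positive, and state how many BLQ values were excluded. The condition is needed because BLQ values are set to 0 in the PD Analysis Set, so the ratio is not automatically positive.

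The cost is a short text edit and matching table shells. No data collection changes. Protocol 9.4.4 needs no amendment, because it names no geometric mean for PD data.

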7.4.3. Pharmacokinetic Parameter Analyses

The following plasma PK parameters, as data permit, will be calculated for total molybdenum and PUF molybdenum (as surrogate measures of ALXN1840 PK) after dosing on Days 1, 25, 29 and 39 using noncompartmental methods with Phoenix® WinNonlin® (Certara USA Inc., Princeton, New Jersey) Version 8.0 or higher or SAS Version 9.4 or higher (SAS Institute Inc., Cary, North Carolina), as applicable. Calculations will be based on the individual actual sampling times relative to the actual ALXN1840 reference dosing times recorded during the study.

- Time delay between the time of dosing and time of appearance of molybdenum concentration (T_{lag}) in plasma
- Maximum observed concentration (C_{max})
- Dose-normalized C_{max} (C_{max_n}); n = dose normalized
- Time to maximum concentration (T_{max})
- Trough (pre-dose) concentration observed at the start of the dosing interval (C_{trough})
- Time of last quantifiable concentration (T_{last})
- Observed concentration at the end of the dosing interval (C_{τ} , where $\tau = 24$ h)
- Area under the plasma concentration versus time curve (AUC) from time 0 to the last quantifiable concentration (AUC_t)
- Dose-normalized AUC_{t_n} (AUC_{t_n}); n = dose normalized
- AUC from time 0 to infinity (AUC_{∞}) (Day 1 only)
- Dose-normalized AUC_{∞} (AUC_{∞_n}); n = dose normalized
- AUC over the dosing interval (AUC_{τ})
- Accumulation ratio (AR) calculated as C_{max} , C_{trough} , and AUC_{τ} after repeat dosing divided by those after initial dosing on Day 1:

For 15 mg/day:

- $C_{max,Day25}/C_{max,Day1}$
- $C_{trough,Day26}/C_{trough,Day2}$
- $AUC_{\tau,Day25}/AUC_{\tau,Day1}$

For 30 mg/day:

- $C_{max,Day39}/C_{max,Day29,adjusted}$
- $C_{trough,Day40}/C_{trough,Day30,adjusted}$
- $AUC_{\tau,Day39}/AUC_{\tau,Day29,adjusted}$

Note: total molybdenum and PUF molybdenum concentration-time profiles on Day 28 after the last 15 mg ALXN1840 dose will be extrapolated to Day 29 (0-24 hr) and subtracted from the

observed Day 29 concentration-time profiles after the first 30 mg ALXN1840 dose for the estimation of the $C_{\max, \text{Day}29, \text{adjusted}}$, $C_{\text{trough}, \text{Day}30, \text{adjusted}}$, and $AUC_{\tau, \text{Day}29, \text{adjusted}}$.

- Apparent terminal phase elimination rate constant (λ_z)
- Terminal elimination half-life ($t_{1/2}$)
- Apparent total body clearance (CL/F) of ALXN1840 from plasma
- Apparent volume of distribution (V_d/F)

For ALXN1840, equivalent molybdenum dose will be used to calculate total molybdenum CL/F and V_d/F values as described in Section 7.2.2. For ALXN1840 30 mg equivalent molybdenum dose is 6.66 mg.

Additional plasma PK parameters may be calculated if deemed appropriate.

For the PK analysis, values below the limit of quantification (BLQ) prior to the first measurable concentration will be set to zero whereas the rest of all other BLQ values will be treated as missing.

Pharmacokinetic parameters derived from plasma concentrations of total molybdenum and PUF molybdenum will be presented in data listings and summarized by analyte, treatment (dose), and day using the following descriptive statistics: number of participants, arithmetic mean, SD, arithmetic CV, GM, GMCV, 95% CI, median, minimum, and maximum. Geometric mean and geometric CV will be presented for C_{\max} and AUCs only. When calculating the geometric mean, values of 0 will be discarded.

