1.2. Schema

Figure 1: Study Schematic

- Participants eligible for the study will be enrolled on Day -7 and initiated on a copper- and molybdenum-controlled diet, which will be continued during Treatment Period 1 and Treatment Period 2 when in the CRU, through Day 39.
- Participants will be admitted to the CRU for Treatment Period 1 on Day -8 and may be discharged on Day 9 or remain in the CRU for their own safety or to maintain the integrity of the conduct of the study. Participants who are discharged will be re-admitted on Day 22 or Day 23 for Treatment Period 2 and will remain in house until Day 40. To ensure flexibility, the Outpatient Period may be extended up to an additional 14 days with Investigator approval. In this situation, participants will be given additional investigational product to support daily dosing throughout the Outpatient Period. In such cases, the actual Outpatient Period duration will be recorded and the participant will continue Inpatient Period 2 at Day 23.
- Participants will be administered ALXN1840 at a dose of 15 mg/day on Day 1 through Day 28 and then increase to 30 mg/day on Day 29 through Day 39. During the Outpatient Period, participants will use SMS text messaging to confirm study intervention administration.
- Participants will have 3 intake and output collection periods including:
 - Baseline Day -4 through Day -1
 - Day 1 through Day 8 (I/O for 15 mg)
 - Day 25 through Day 39 (Days 25 through 28, I/O for 15 mg; Days 29 through 39, I/O for 30 mg)
- During these periods all intake (including food and drink) and output (including urine and feces) will be collected and assessed for copper and molybdenum.
- Blood sampling for PK/PD will be as follows:
 - PK/PD collection (24-hour): Days 1, 25, 29, and 39
 - Pre-dose PK/PD sampling days: Days 4 - 7, Days 26 - 28, Days 30 - 38
 - End of Study Visit Day 54 +/- 2 days

Abbreviations: AP = accumulation period; CRU = clinical research unit; EOS = End of Study; I/O = input/output; PD = pharmacodynamic; PK = pharmacokinetic; SS = steady state.

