Following single-dose administration of 60 mg ALXN1840, total molybdenum peaked at approximately 4.54 hours with a terminal elimination half-life measured at approximately 51 hours. In Study WTX101-201, the PK of ALXN1840, based on total molybdenum, indicated that exposure in participants with WD at a dose of 30 mg appeared consistent with previous results from healthy participants. The half-life was estimated to be approximately 24 hours at steady state on Days 84 and 168 and was shorter than estimated in previous studies. Based on a total molybdenum PK half-life of approximately 24 - 51 hours, total molybdenum steady state may conservatively be reached within approximately 10 - 12 days. Nevertheless, results (as

measured by total molybdenum) obtained from the ALXN1840 balance study in the LEC WD rat model suggested that approximately 30% of a single dose of ALXN1840 remained in the liver by Day 7, indicating the possibility of tissue accumulation, particularly in the setting of high liver copper concentration ([Plitz, 2019](#)).

If the half-life of ALXN1840 in liver were longer than that of the systemic compartment, the accumulation may not be readily detected in the absence of a longer treatment period and with characterization of the terminal elimination period. An alternative approach to assessing steady state using total molybdenum PK is to assess whether the total molybdenum intake is equal to the total molybdenum output; this approach may detect any significant ongoing accumulation in the liver or other tissues.

Detailed descriptions of the chemistry, pharmacology, efficacy, and safety of ALXN1840 are provided in the Investigator's Brochure (IB).

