5.1.2. Secondary Objectives and Endpoints

The secondary objectives and endpoints are given below. Molybdenum balance measurements are conducted in a similar manner to copper balance measurements (Section 5.1.1.1).

Objectives	Endpoints
Assess change in copper balance in response to ALXN1840 15 mg/day and 30 mg/day during ALXN1840 accumulation and at steady state periods versus the pretreatment Baseline in participants with WD	Change in mean daily copper balance as measured by the calculated difference between copper intake (in food and drink) and copper output (in feces and urine) from pretreatment Baseline (Days -4 through -1) and ALXN1840 accumulation and steady-state periods for each dose
Investigate the effect of ALXN1840 (15 mg/day and 30 mg/day) on the disposition of copper in participants with Wilson Disease (WD)	Copper quantified in food, drink, feces, and urine, including plasma total and labile bound copper (LBC) during ALXN1840 accumulation and steady-state periods for each dose
Investigate the effect of ALXN1840 on the disposition of molybdenum at steady state at 15 mg/day and 30 mg/day in participants with WD	Molybdenum quantified in food, drink, feces, and urine, plasma total molybdenum at ALXN1840 steady state
Assess steady-state total molybdenum balance as a measure of ALXN1840 15 mg/day and 30 mg/day in participants with WD	Mean daily molybdenum balance as demonstrated through measurement of molybdenum intake (in food, drink, and ALXN1840), and molybdenum output (feces and urine) representing ALXN1840 steady state
Assess accumulation of molybdenum with ALXN1840 treatment at 15 mg/day and 30 mg/day in participants with WD	Accumulation of molybdenum as determined by molybdenum balance
Determine the steady-state plasma pharmacokinetic (PK) of total molybdenum and plasma ultrafiltrate (PUF) molybdenum (as surrogate measures of ALXN1840, 15 mg and 30 mg) in participants with WD	PK parameters for plasma total and PUF molybdenum

Note: The accumulation period refers to time from initiation of ALXN1840 (Day 1) to expected steady state at Day 10, based on 5 times the half-life of 2 days.

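### SAP 7.4.3 does not limit CL/F and Vd/F to steady-state days, so the Day 29 values at 30 mg would be overstated and clearance would appear to fall by Day 39

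*SAP*

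**What the plan says.** SAP 7.4.3 opens its list with "The following plasma PK parameters, as data permit, will be calculated" for total and ultrafiltrate molybdenum, "after dosing on Days 1, 25, 29 and 39 using noncompartmental methods". The list includes "Apparent total body clearance (CL/F) of ALXN1840 from plasma", and then Vd/F. Neither carries a day restriction or a formula. AUC to infinity, by contrast, is marked for Day 1 only.

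The section fixes the dose for these parameters: "For ALXN1840 30 mg equivalent molybdenum dose is 6.66 mg". It summarises parameters by analyte, dose and day, so Day 29 and Day 39 become two separate 30 mg rows. It also describes subtracting the extrapolated Day 28 profile from the Day 29 profile, but only to obtain the adjusted Cmax, Ctrough and AUCtau for the accumulation ratios.

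Protocol 1.2 gives the dosing as "15 mg/day on Day 1 through Day 28 and then increase to 30 mg/day on Day 29 through Day 39". Protocol 9.4.4 lists CL/F and Vd/F without naming days, so it supplies no restriction either.

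**The concern.** Dose divided by the AUC over one dosing interval equals apparent clearance only at steady state. On Day 29 plasma molybdenum is moving from the 15 mg plateau to the 30 mg plateau. The plan itself expects that to take about ten days ("based on 5 times the half-life of 2 days"). The numerator is the full 30 mg dose, while the denominator still largely reflects 15 mg dosing.

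The SAP leaves no valid basis for a Day 29 clearance. With AUC to infinity confined to Day 1, the only unadjusted Day 29 AUCs run from 0 to 24 h.

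PK parameters are a secondary endpoint. A reader of the by-day table would see 30 mg clearance drop between Day 29 and Day 39 and could take it for time-dependent kinetics. Vd/F, being CL/F divided by lambda_z, carries the same bias.

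**Working it through.** **Inputs.** Dose sequence and profile days: Protocol 1.2. Dosing interval: 24 h. Half-life: "Based on a total molybdenum PK half-life of approximately 24 - 51 hours" (Protocol 2.2). Time to peak: "total molybdenum peaked at approximately 4.54 hours" (Protocol 2.2). Sampling times -0.5, 2, 4, 5, 6, 8, 12 and 24 h: Protocol Table 2. Assumed, because the documents do not state it: CL/F = dose/AUCtau, linear one-compartment kinetics, no dietary molybdenum.

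**The plan's own figures.** Molybdenum per tablet: 95.96/432.54 x 15 = 3.328 mg, rounded to 3.33; two tablets give 6.66 mg, as stated. Time to steady state: 5 x 2 days = 10 days; at 51 h, 5 x 51/24 = 10.6 days.

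**Closed form (bolus input).** Let D be the 15 mg dose and x = exp(-ln2 x 24/half-life), the fraction left after one interval. By Day 28 the 15 mg plateau is reached, with AUCtau = D/CL. On Day 29:
- carry-over from the 15 mg doses: (D/CL) x
- the new 30 mg dose: (2D/CL)(1 - x)
- total: (D/CL)(2 - x)

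So reported/true CL/F on Day 29 = 2/(2 - x). At 24 h, x = 0.500 and the ratio is 2/1.500 = 1.333. At 51 h, x = 0.722 and the ratio is 2/1.278 = 1.565. For Day 39, the eleventh 30 mg dose, x is replaced by x^11, giving 1.0002 and 1.014.

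**Oral input.** First-order absorption, with the rate set so that a single dose peaks at 4.54 h; superposition of 28 doses of D and then 11 of 2D. Ratios of reported to true CL/F:

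| Half-life | Day 29, bolus | Day 25, oral | Day 29, oral | Day 39, oral | Apparent fall, Day 29 to 39 |
|---|---|---|---|---|---|
| 24 h | 1.333 | 1.000 | 1.352 | 1.000 | 26% |
| 36 h | 1.460 | 1.000 | 1.475 | 1.003 | 32% |
| 48 h | 1.547 | 1.000 | 1.560 | 1.011 | 35% |
| 51 h | 1.565 | 1.000 | 1.578 | 1.014 | 36% |

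The fall is 1 minus (Day 39 ratio/Day 29 ratio); at 51 h, 1 - 1.014/1.578 = 0.357. A linear trapezoid on the planned sampling times, with predose taken as time 0, changes little: Day 29 ratios are 1.358 (24 h) to 1.586 (51 h).

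**Using the carry-over-adjusted Day 29 AUCtau.** Subtraction leaves only the new dose's first 24 h, so the bolus ratio is 1/(1 - x): 2.00 to 3.59. With oral input it is 2.084 to 3.734, an overstatement of 108% to 273%. The adjustment makes clearance worse.

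**Day 1.** Dose/AUCtau after the first 15 mg dose has that same 2.084 to 3.734 ratio, so Day 1 needs AUC to infinity. From a 24 h profile, 52% (24 h) to 73% (51 h) of that area is extrapolated.

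**The case against.** The list is qualified by data availability and no formula is given, so the PK analyst might simply not compute a Day 29 clearance. But the Day 29 profile is fully sampled, so the data do permit the calculation; the problem is validity. What stands is that the size depends on the formula. Dose over AUC to infinity on the unadjusted Day 29 profile would instead understate CL/F, with bolus ratio 2/(2 + x/(1 - x)): 0.667 to 0.435, or 33% to 56% too low. The SAP does not provide that AUC for Day 29, but the direction is conditional on reading CL/F as dose/AUCtau.

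The upper figure of 58% uses the 51 h half-life seen after a single 60 mg dose. In participants with Wilson disease at steady state, Protocol 2.2 reports about 24 h, which gives 35%. That is fair, and the range should be read with it in mind.

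The consequence is also small. The secondary objective is steady-state PK, the study is descriptive with about 10 participants, SAP 7.4.5 assesses dose proportionality on Days 25 and 39 only, and no planned analysis uses Day 29 CL/F. All of that stands.

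A reader might go further and infer that the half-life from these 24 h profiles is mostly noise, that the accumulation and steady-state windows are thereby undermined, and that an accumulation half-life from the Day 25/Day 1 AUCtau ratio should replace it. The documents do not support this:
- The windows are fixed calendar days, set in advance from a prior half-life of 2 days. The half-life estimated here feeds none of them.
- Precision depends on a residual CV that the documents do not give. With the 8, 12 and 24 h points and an assumed 5% CV, the 90% range is 19-32 h for a true 24 h and 34-105 h for a true 51 h. At an assumed 10% it is 16-47 h for 24 h; for 51 h it runs from 25 h to no finite value, with about 5% of slopes non-positive.
- The accumulation formula needs the same kinetics on Day 1 and Day 25. If the reported 51 h (single dose) and 24 h (steady state) both hold with equal volume and bolus input, the ratio is R = (24/51)/(1 - 0.722) = 1.69. Then ln2 x 24/ln(R/(R - 1)) = 18.6 h, which matches neither.

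**Conclusion.** The point holds as a defect of specification in SAP 7.4.3. Followed as written, and with CL/F read as dose/AUCtau, the SAP produces a Day 29 clearance at 30 mg that is about 35% (half-life 24 h) to 58% (51 h) too high, against at most 1.4% on Day 39. The result is a false 26-36% fall between the two 30 mg rows. Vd/F inherits the bias. The carry-over adjustment does not repair this and would enlarge it.

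The figures apply to total molybdenum; the documents give no half-life for ultrafiltrate molybdenum. The damage is confined to the descriptive PK parameter table. On half-life, the most that can be said is that lambda_z from 24 h profiles is imprecise when the true value is near 51 h, to a degree set by an unstated residual CV.

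**What to change.** In SAP 7.4.3:
- state CL/F = molybdenum dose/AUCtau;
- restrict AUCtau-based CL/F and Vd/F to Day 25 (15 mg) and Day 39 (30 mg);
- drop both for Day 29;
- base any Day 1 value on AUC to infinity and report its extrapolated fraction.

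Under the same model this reduces the error in the 30 mg CL/F from 35-58% to at most 1.4%. The cost is SAP wording and the loss of an uninterpretable Day 29 row. No sample, visit or other analysis changes. The lambda_z half-life can stay, with a note on its imprecision.
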